2.5. Sample size

The sample size for the development of the Pediatric Pain Screening Tool included 321 children aged 8-18 years old ²⁸. A minimum of 100 subjects is required for a stable variance-covariance matrix ⁴⁵, and following the rule of thumb of at least 10 events for variable (or items within the prognostic tool) ⁴⁵, around 300 individuals would be necessary for a maximum of 30 items included in the tool. However, in case of presence of binary predictors with low prevalence, ≥ 20 events per variable would be necessary ⁴⁶ (this would consequently lower the number of items that it is possible to include in the prognostic tool).

Previous studies have shown an annual consultation prevalence of 104 - 200 per 10,000 registered persons in children aged 3 to 19 years old ^{24,25,47}. Here below, different potential scenarios about participants' recruitment are described. These scenarios are calculated on a conservative estimate of 30% study participation rate. This is a worst-case scenario, and this approach is taken in order to have a safe recruitment that will provide us with enough children and adolescents for the development of the tool.

Based on the prevalence estimate of 119 ²⁴ per 10,000 registered persons (which is a likely prevalence for children aged 8-19), at least 168 general practices of a medium size of 5000 individuals each will be needed to recruit at least 300 participants at baseline (provided that 30% of all children aged 8-19 with a consultation for knee pain during a period of 6 month decide to take part in the study). This means that the overall target population includes 840.000 persons (168*5000) registered in general practices, which corresponds to 1/7 of the whole Danish population. Indeed, among these 840.000 persons, approximately 168.000 (20%) will be aged between 8 and 19 years old and 1,999 (119 per 10,000 registered persons) of these young people will have a consultation for knee pain in one year. Of these, 999 will have a consultation in a 6-

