month period (which is the duration of the baseline recruitment). If 30% of these children decide to take part in the study, there will be data on 300 children aged 8-19 at baseline. However, for the development of the START-BACK screening tool 244 patients were identified, of which only 131 (54%) returned the baseline questionnaire and 107 (82%) agreed to further contact ²⁹. Therefore, if we aimed at only 100 children aged 8-19 years old with a consultation for knee pain in a 6-month period and by keeping the same proportions shown above (i.e. only 30% baseline participation rate), only 56 general practices of a medium size of 5000 individuals each would be needed (corresponding to a target population of 280.000 individuals, of which 56.000 aged 8-19 years old). A target of 100 children would enable approximately 30 individuals in each prognostic risk group (low/medium/high).

Conversely, based on the highest prevalence estimate (200 per 10,000 registered persons) and considering a 30% participation rate into the study, 33 general practices of a medium size of 5000 individuals each would be needed (corresponding to a target population of 165.000 individuals, of which 33.000 aged 8-19 years old) to recruit at least 100 children. To recruit at least 300 children, 100 general practices of a medium size of 5000 individuals each would be needed (corresponding to a target population of 500.000 individuals, of which 100.000 aged 8-19 years old). Alternatively, it might be possible to target fewer bigger general practices (e.g. 18 general practices of a medium size of 10.000 individuals to recruit 100 children).

In addition, if only 100 children will be recruited from general practices, it might be possible to perform an extra recruitment through social media that would complement the group of children recruited through general practices, in order to achieve a total sample size of at least 300 children. In this case, sensitivity analysis would be performed to check for any potential difference in characteristics between the sample recruited through general practices and social media.

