12. Har du røget cigaretter i de sidste 4 uger?	 Nej  Ja
13. Hvor enig er du i dette udsagn "Jeg har problemer med at sove" (det behøver ikke nødvendigvis være på grund af smerter)	 Aldrig  Næsten aldrig  Nogle gange  Ofte  Næsten altid

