2.10. Analysis plan

The analysis plan that will lead to the development of the final prognostic tool will include the following stages:

1. Descriptive analysis of the collected data. Results will be presented as means with SDs and as percentages.
2. Assessment of potential floor and ceiling effects of the items included in the prognostic tool. This will be done by checking that for those items that represent an ordinal or categorical variable with more than two potential response categories, the responses given are not skewed towards the top or bottom extreme of the scales (e.g. a ceiling or floor effect is present if >15% of the respondents report the lowest/highest score of the scale ^{42,45,57}).
3. Estimation of knee pain prognosis (i.e. recurrence/persistence of knee pain, dichotomous outcome) at 3-month and 6-month follow-up by means of multiple logistic regression to estimate ORs and 95% confidence intervals for each item included in the tool. This will inform on which factors are most related to the prognosis of knee pain and will provide an insight on the scores of the prognostic tool (both overall and for subscales) to be applied for the creation of the initial risk groups. Alternatively, the RR will be estimated if a general linear model analysis will be carried out.
4. Discriminant validity of the prognostic score will be assessed by using receiver operating characteristics (ROC) curves and by calculating the area under the curve (AUC) for the overall score and subscales of the prognostic tool.

[figure not shown]
5. Creation of risk groups for the recurrence/persistence of knee pain on the basis of cut-off scores identified using the ROC curves for the overall tool score. The initial idea is to have three risk groups (low/medium/high), which have to be clinically meaningful. More importance will be given to the sensitivity of the tool over the specificity.
6. Assessment of the predictive ability of the risk groups defined at baseline by calculating the sensitivity, specificity and negative and positive likelihood ratios (LRs) against the primary and secondary outcome (i.e. 3-month and 6-month recurrence/persistence of knee pain; disability/activities limitation due to knee pain).
7. Assessment of the potential influence of non-modifiable patients' characteristics on the predictive ability of the risk groups defined at baseline by stratifying the former analysis by age groups and sex.

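### If recruitment stops at the 100-child scenario, the plan's own 10-events-per-item rule cannot be met for the 13-item logistic model, and section 2.10 gives no fallback

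*Combined protocol and SAP*

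**What the plan says.** Section 2.5 (Sample size) states two numerical criteria. One is "A minimum of 100 subjects is required for a stable variance-covariance matrix". The other is a rule for the model, "following the rule of thumb of at least 10 events for variable (or items within the prognostic tool"), which the section turns into a number of children: "around 300 individuals would be necessary for a maximum of 30 items included in the tool". A stricter version follows: "in case of presence of binary predictors with low prevalence, ≥ 20 events per variable would be necessary".

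The section then costs several recruitment scenarios. It leads with 300 children at baseline. After describing how many patients responded in the START-BACK development study, it turns to a smaller number: "Therefore, if we aimed at only 100 children aged 8-19 years old with a consultation for knee pain in a 6-month period". This is costed at 56 or 33 practices of 5,000, or 18 of 10,000, and is said to give about 30 children in each of three risk groups. If practices yield only 100, recruitment through social media to reach 300 is mentioned as a possibility, not as a commitment.

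Section 2.6 prints the questionnaire, described there as the final tool, with questions numbered 1 to 13. Step 3 of section 2.10 analyses the dichotomous outcome "by means of multiple logistic regression to estimate ORs and 95% confidence intervals for each item included in the tool". Its results inform the scores and the initial risk groups.

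**The concern.** The 10-events rule is the only criterion in section 2.5 that concerns a regression with many predictors, and it is used for 300 but never applied to 100. The reasons the text gives for 100 are a precedent from another tool and a count per risk group. Neither says whether 13 items can be estimated together. The covariance-matrix minimum does not say so either, and no step in section 2.10 analyses such a matrix.

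Steps 4 to 6 of section 2.10 build the AUC, the cut-offs and the risk groups on a score informed by step 3. With too few events per term, coefficients tend to be too large and unstable, and the score looks better in the development sample than it will in new children. Section 2.10 lists no item-reduction rule, penalisation, shrinkage or internal validation that would correct this. Section 1.1 itself warns that misclassified patients may be undertreated or overtreated.

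**Working it through.** **1. The plan's own figures.** Expected recruits = practices × practice size × 0.20 (share aged 8–19) × annual consultation rate × 0.5 year × 0.30 (participation), all from section 2.5.

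- 168 × 5,000 × 0.20 × 0.0119 × 0.5 × 0.30 = 299.9 (stated 300)
- 56 × 5,000 × 0.20 × 0.0119 × 0.5 × 0.30 = 100.0 (stated 100)
- 33 × 5,000 × 0.20 × 0.0200 × 0.5 × 0.30 = 99 (stated 100)
- 100 × 5,000 × 0.20 × 0.0200 × 0.5 × 0.30 = 300 (stated 300)
- 18 × 10,000 × 0.20 × 0.0200 × 0.5 × 0.30 = 108 (stated 100, rounded up)
- Per risk group: 100 / 3 = 33.3 (stated about 30)
- Rule: 30 items × 10 = 300, which holds only if every child counts as an event

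The recruitment arithmetic is sound. The question is what 100 children can support.

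**2. Events required, at one model term per item.**

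- 13 numbered items: 13 × 10 = 130
- 15 answers (items 9 and 10 each hold two questions): 15 × 10 = 150
- 11 items, if age and sex are kept out of the model because step 7 stratifies by them: 11 × 10 = 110

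All three exceed 100. Entering multi-category items as several terms would raise the requirement. If the 20-event rule applied throughout, 13 × 20 = 260. Item 12, "12. Har du røget cigaretter i de sidste 4 uger", is the kind of binary item that might trigger that rule, but the documents give no prevalence for it.

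**3. Events available from 100 children.** The documents give no 3-month rate of activity-limiting knee pain. The nearest figure, in section 1.1, is that about 50% of adolescents still report knee pain after 1 or 2 years. A range of 30–70% is assumed here, with no loss to follow-up. Since a logistic model needs both outcomes, the smaller class is shown as well.

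| Assumed outcome rate | Events | Events / 13 | Smaller class | Smaller class / 13 | Smaller class / 15 |
|---|---|---|---|---|---|
| 30% | 30 | 2.3 | 30 | 2.3 | 2.0 |
| 40% | 40 | 3.1 | 40 | 3.1 | 2.7 |
| 50% | 50 | 3.8 | 50 | 3.8 | 3.3 |
| 60% | 60 | 4.6 | 40 | 3.1 | 2.7 |
| 70% | 70 | 5.4 | 30 | 2.3 | 2.0 |

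The arithmetic ceiling is 100 / 13 = 7.7, if every child had the outcome. It is only a bound, because no model could then be fitted.

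**4. Loss to follow-up.** Section 2.5 makes no allowance for it. Borrowing 107 / 131 = 82% (START-BACK patients who agreed to further contact) purely as an illustrative retention figure, 100 × 0.82 × 0.50 ≈ 41 events, and 41 / 13 ≈ 3.1 per item.

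**5. What would meet the rule.** At a 50% rate, 100 children support 50 / 10 = 5 terms. To reach 130 events, 130 / 0.50 = 260 children with outcome data are needed; at 30% the number is 434, and at 70% it is 186.

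**6. Illustrative consequence.** A logistic model was simulated with 13 or 15 independent standardised predictors, five of them prognostic (coefficient 0.45, OR 1.57 per SD), and 30–50% events. At 100 children the true coefficients were overestimated by roughly 20–30%, and the calibration slope in new children was about 0.36–0.45, against 0.69–0.74 at 300. Mean AUC in new children was 0.67–0.68, against 0.71–0.72 at 300 and a best achievable value of about 0.74. These effect sizes are invented, so the results show direction and rough scale only.

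**The case against.** The strongest defence is that 100 is not the planned size. Section 2.5 presents scenarios, leads with 300, words 100 conditionally, and mentions a top-up to 300. That is a fair reading, and the point is limited to recruitment stopping near 100. It survives because the section also calls 100 a target, the top-up is not a commitment, and nothing in section 2.10 changes if it does not happen.

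Two stronger readings are tempting and are not supported:

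- A reader might infer that the plan declares 100 safe or sufficient. The remark about safe recruitment in section 2.5 refers to the conservative 30% participation assumption used for all scenarios, and it comes before 100 is raised as a target.
- A reader might infer that 100 was derived from the covariance-matrix minimum, because the numbers match. The text ties 100 to the START-BACK precedent and the risk-group count. It never makes the other link.

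The item list may also be less fixed than section 2.6 suggests. Section 2.10 says its analyses will lead to the final tool, and section 2.5 accepts that low-prevalence binary predictors would reduce the number of items. But no procedure for removing items is written down, and step 3 asks for an odds ratio for each one. The alternative of risk ratios, also in step 3, uses the same items and children.

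Finally, the AUC loss in the simulation is modest, and at 130 children the slope was still only about 0.5. Meeting a rule of thumb does not by itself make the model reliable. That limits how much weight the 10-per-item line can bear, but it does not help the 100-child scenario.

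**Conclusion.** The point holds for the case where recruitment stops near 100. The shortfall against the plan's own rule is arithmetic and needs no outcome rate: at least 130 events for 13 items (110 even without age and sex) cannot come from 100 children. In usable terms the smaller outcome class gives at most 3.8 per item, and 2.3 if the assumed rate is 30% or 70%, against 10 required. This rests on one term per item and complete follow-up, both of which favour the plan.

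The practical consequence is that item odds ratios, and the scores and risk groups informed by them, would be overfitted with nothing planned to correct it. How badly depends on unknown effect sizes. The finding does not show that the 300-child scenario fails. There the rule is met for 13 items if at least 130 analysed children have the outcome (130 / 300 = 43%). The change is worth making, but it concerns a fallback scenario and not the whole design.

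**What to change.** **Section 2.5.** State that 100 children do not meet the 10-events-per-item rule for the 13-item model, and label 100 as a feasibility target. Add that the 100-subject covariance-matrix minimum does not size the logistic model.

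**Section 2.10, step 3.** Add a rule based on the children actually analysed: fit the full unpenalised item model only if the smaller of events and non-events is at least 10 per model term. Otherwise either fit all items with a penalised model (for example ridge), or fit a reduced set ranked in advance from the literature review in section 2.6 (about 5 terms at 100 children and 50% events). Name the chosen option before outcome data are seen, and report the resulting tool as preliminary.

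**Cost.** Wording in two sections and no extra children. In the small-sample scenario fewer items get their own unpenalised odds ratio. The rule can also apply at 300: with a 40% outcome rate, 120 / 13 = 9.2 per item, so the fallback would be used there too. Penalisation and pre-ranking are two reasonable choices among several; what matters is that one is fixed in advance.

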2.6. Development of the tool

Clinically meaningful prognostic factors for knee pain in children and adolescents were identified from a review of the current literature on the topic. Initially, the most important domains for the prognosis of knee pain and the specific items to be included in the tool were selected based on the strength of association from previous studies identified within the literature and from meta-analysis of individual participant data. Additional factors were included after discussion with general practitioners that agreed to take part to the study and staff working at the Center for General Practice at Aalborg University. During this stage, great emphasis was given to include only the most necessary factors taking in mind that the prognostic tool should be used in a reasonable time of a consultation within general practice.

Items relative to the specific prognostic factors were initially selected from validated scales where possible (e.g. regarding pain characteristics, limitation in daily activities, sport participation, psychological factors). When multiple items within a scale or multiple scales were available for a prognostic factor, the relevant literature on the topic was identified and discussed at meetings with general practitioners and staff working at the Center of General Practice at Aalborg University in order to select the most appropriate items within the possible options. Following previous tools developed for pain in children and adolescents^{28,48,49}, items were properly worded for the age and properly framed with respect to the response options (e.g. direction, time intervals, avoiding double-barreled items).

The initial version of the tool was tested and implemented during the pilot stage (great emphasis was given to the cognitive interviews that were carried out with children and adolescents), until reaching a final version that will be used for the collection of the data, as further described below in section 2.8.6. The outline of the final tool is provided in the figure below:

Knæ project

Disse spørgsmål handler om dine knæsmerter. Sæt kryds i den boks som bedst beskriver hvordan du har det, eller skriv i tekstdokumentet. Hvis du er i tvivl, så bedes du svare så godt du kan. Spørgsmålene står i venstre side, og svarmulighederne i højre side af skemaet.

Navn	
1. Hvor gammel er du?	(_____)
2. Er du en pige eller en dreng?	 Pige  Dreng
3. Har du ondt i det ene knæ eller begge knæ?	 Kun det ene knæ (højre knæ)  Kun det ene knæ (venstre knæ)  Begge knæ
4. Hvor lang tid har du haft ondt i knæet? Hvis du har ondt i begge knæ skal du svare ud fra det knæ hvor smerterne har varet længst	 under 3 måneder  3–6 måneder  6–12 måneder  mere end 12 måneder (hvor mange år? _____)
5. Hvordan startede dine knæsmerter? Hvis du har ondt i begge knæ skal du svare ud fra det knæ hvor smerterne har varet længst	 Kom pludseligt (f.eks. da jeg fik en skade)  Kom gradvist (f.eks. langsomt over en længere periode)
6. Hvor ofte oplever du dine knæsmerter? Hvis du har ondt i begge knæ skal du svare ud fra det knæ hvor smerterne har varet længst	 Sjældent  Månedligt  Ugentligt  Mere end en gang om ugen  Næsten dagligt
7. Har du ondt andre steder i kroppen som gør at du ikke kan deltage i dine normale aktiviteter (leg i skolegården, sport og lignende)? I dette spørgsmål menes andre steder end knæet	 Nej  Ja. Marker venligst hvor. Du må gerne afkrydse mere end et område:  Hovedet  Ryg eller nakke  Skulder  Albuen  Håndled eller hånden  Underbenet  Låret  Bækkens (badebuksområdet)  Ankel, hælen eller fodden  Andet (_____)
8. Under hver overskrift bedes du sætte kryds i DEN kasse, der bedst beskriver hvordan dine knæsmerter påvirker de ting du laver på en normal dag (f.eks., gå i skole, hobbyer, sport, være sammen med venner eller familie) Hvis du har ondt i begge knæ skal du svare ud fra det knæ hvor smerterne har varet længst	 Jeg har ingen problemer med at udføre mine sædvanlige aktiviteter  Jeg har lidt problemer med at udføre mine sædvanlige aktiviteter  Jeg har nogle problemer med at udføre mine sædvanlige aktiviteter  Jeg har store problemer med at udføre mine sædvanlige aktiviteter  Jeg kan ikke udføre mine sædvanlige aktiviteter
9. Hvor enig er du i dette udsagn "Når jeg har ondt, er det forfærdeligt og jeg tror aldrig det bliver bedre" Sæt kryds i den kasse som bedst beskriver hvordan du har det i dag. Ængstelig/deprimeret svarer til at være ked af det (det handler om hvordan du har det, og ikke nødvendigvis på grund af dine smerter)	 Overhovedet ikke  Lidt  I nogen grad  Meget  Rigtig meget  Jeg er ikke ængstelig eller deprimeret  Jeg er lidt ængstelig eller deprimeret  Jeg er i nogen grad ængstelig eller deprimeret  Jeg er meget ængstelig eller deprimeret  Jeg er ekstremt ængstelig eller deprimeret
10. Har din mor eller stedmor ofte ondt i kroppen? (dette kan både være ondt i hovedet, ryggen, skulderen eller andre steder) Har din far eller stedfar ofte ondt i kroppen? (dette kan både være ondt i hovedet, ryggen, skulderen eller andre steder)	 Nej  Ja  Nej  Ja
11. Hvor mange gange per uge deltager du typisk i sport (udover idræt i skolen)? Hvilken type sport? (feks håndbold, fodbold, svømning, løb). Du må gerne skrive mere end en sport.	 Aldrig  1 gange/uge  2 gange/uge  3 gange/uge  4 gange/uge  5 gange/uge  6 gange/uge  7 eller flere gange/uge (_____)

12. Har du røget cigaretter i de sidste 4 uger?	 Nej  Ja
13. Hvor enig er du i dette udsagn "Jeg har problemer med at sove" (det behøver ikke nødvendigvis være på grund af smerter)	 Aldrig  Næsten aldrig  Nogle gange  Ofte  Næsten altid

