2. Second, a prognostic tool developed for knee pain will include items about factors that are specific to the prognosis of knee pain (e.g. pain duration, previous history of knee pain) and therefore would be more sensitive than other more general pediatric pain tools, such as the PPST. This is important considering that misclassification of patients might potentially lead to undertreat those misclassified as low-risk and overtreat those misclassified as high-risk ³².
3. Third, the subgroup of patients who refer to primary care is usually characterized by a different severity of symptoms compared to general population, second or tertiary care samples, as proposed by the iceberg theory of disease ³³⁻³⁵, and it is recommended that prognostic tools are validated in different care settings ³⁶. Therefore, this research has the opportunity to provide information on the predictive ability of a prognostic tool in primary care compared to studies carried out within other samples of care settings, as it has previously been observed a difference in the efficacy of risk prediction potentially because of differences in patients case mix ³⁷.

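### Item 4's pain-duration boxes both include exactly 6 months and no rule assigns that value: a small, cheaply fixed form error that cannot be repaired from the planned data later

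*Combined protocol and SAP*

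**What the plan says.** Section 2.6 introduces the Danish form as the version for data collection: "The outline of the final tool is provided in the figure below". Item 4 has four boxes. The lowest is "under 3 måneder", the middle two are "3–6 måneder 6–12 måneder", and the highest is "mere end 12 måneder (hvor mange år" followed by a blank. Only the highest box asks for a number.

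The form's general instructions are "Sæt kryds i den boks som bedst beskriver hvordan du har det" (tick the box that fits best) and "Hvis du er i tvivl, så bedes du svare så godt du kan" (if in doubt, answer as well as you can). Neither says where a boundary value goes. The same section states that the response options, including time intervals, were properly framed.

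The background (section 1.1) uses duration as its first example when it argues that a knee tool will include "items about factors that are specific to the prognosis of knee pain (e.g. pain duration, previous history of knee pain"). Step 3 of the analysis plan (section 2.10) uses multiple logistic regression to "estimate ORs and 95% confidence intervals for each item included in the tool", and says that this gives an insight into the scores. It does not say whether duration enters as categories or as one ordinal item.

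**The concern.** The wording of the lowest and highest boxes settles 3 and 12 months. Six months is the only boundary shared by two boxes, so the boxes were evidently meant to be exclusive and one edge was missed. Half a year is also a round figure that a child or parent may well give from memory.

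A child with exactly 6 months of pain can tick either box and follow the instructions. Two such children can then differ on a predictor for no reason related to their knees, and one child could answer differently on two occasions. Neither middle box collects the actual duration, so these children could not be identified, recoded or set aside in a sensitivity analysis. The ambiguity would also carry over into use of the tool in practice.

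**Working it through.** **1. The boundaries, read from item 4.**

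| Duration | Boxes that contain it |
|---|---|
| exactly 3 months | 3–6 only (the lowest box is *under* 3) |
| exactly 6 months | 3–6 and 6–12 |
| exactly 12 months | 6–12 only (the highest box is *more than* 12) |

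This step needs no assumption.

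**2. Sample size.** The plan gives no figure on this point, so I take its target of 300. Section 2.5's own scenario reproduces it: 168 × 5,000 × 0.20 × 119/10,000 × 0.5 × 0.30 = 299.9.

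**3. Effect on the odds ratio (OR) between the two boxes.** All inputs here except the 300 are assumptions. They are: 60 children (20%) clearly in each box; event risks of 40% v 50% (OR 1.50) or 40% v 60% (OR 2.25); and a further 2%, 5% or 10% at 6 months (m = 6, 15 or 30 children).

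The risk in a box is the weighted mean of its members' risks, and OR = odds(upper)/odds(lower).

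Worked case: m = 15, risks 40% v 50%, 6-month children midway at 45%.

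- Overlapping boxes, even split of 7.5 each. Lower: (60×0.40 + 7.5×0.45)/67.5 = 0.4056. Upper: (60×0.50 + 7.5×0.45)/67.5 = 0.4944. OR = 1.43.
- Exclusive boxes, 6 months in the upper box. Lower: 0.40. Upper: (60×0.50 + 15×0.45)/75 = 0.49. OR = 1.44.

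Worst case, same m: the 6-month children carry the full upper-box risk and all tick the lower box. Lower: (60×0.40 + 15×0.50)/75 = 0.42. OR = 1.00/0.7241 = 1.38, against 1.50.

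| OR with no 6-month children | m | Midway risk, overlap | Midway risk, exclusive | Worst case |
|---|---|---|---|---|
| 1.50 | 6 | 1.471 | 1.473 | 1.44 |
| 1.50 | 15 | 1.434 | 1.441 | 1.38 |
| 1.50 | 30 | 1.383 | 1.403 | 1.31 |
| 2.25 | 6 | 2.163 | 2.167 | 2.09 |
| 2.25 | 15 | 2.052 | 2.071 | 1.91 |
| 2.25 | 30 | 1.907 | 1.962 | 1.71 |

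With midway risk the overlap costs at most 0.020 on the smaller OR and 0.055 on the larger. The worst case lowers the OR by about 4% to 24%.

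**4. Sampling error, 60 v 60.** For 40% v 50%, SE(log OR) = √(1/24 + 1/36 + 1/30 + 1/30) = 0.369, so the 95% interval around 1.50 is 0.73 to 3.09. For 40% v 60% it is 1.08 to 4.67 around 2.25. Every shift above lies inside its interval.

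**5. Effect on discrimination.** Assume box shares of 35/20/20/25% and ORs of 1, 1.5, 2.25 and 3.4. At a base risk of 40% the box risks are 0.40, 0.50, 0.60 and 0.694. Exclusive boxes give an area under the curve (AUC) of 0.6308 for the item alone. Now let 10% of children be at 6 months with the full 6–12 risk, half of them ticking 3–6. The shares become 35/25/15/25%, the 3–6 risk becomes (20×0.50 + 5×0.60)/25 = 0.52, and the AUC is 0.6288. The loss is 0.002. With midway risk it is 0.0005 or less.

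**The case against.** A reader might infer that the overlap distorts the duration odds ratios and, through them, the prognostic score. The case against that reading is strong, and most of it stands.

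- **The size depends on an assumed jump in risk.** A fall in the ratio between the two boxes from 1.5 to about 1.4 can be attributed to the overlap only if every 6-month child carries the full 6–12 risk. If risk rises gradually, these children resemble both neighbours, and exclusive boxes give almost the same ratio.
- **The link to the score is loose.** Step 3 says only that the regression gives an insight into the scores. If duration is one ordinal item, there is no separate odds ratio at this boundary. Steps 4 and 5 use the overall score from a form with 13 numbered items.
- **The share of children affected is unknown.** Any figure, including 15 to 30 of 300, is an assumption.
- **The form was tested.** Sections 2.8.6 and 2.8.7 describe cognitive interviews, retesting, and a stability pilot before and after consultation, where inconsistent answers could have shown up. No results are given, so the pilots neither clear item 4 nor convict it.
- **The fix is partial.** A child with 5 or 7 months of pain who recalls half a year will still be placed by rounding.

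One part of the defence fails. Asking for the best-fitting box does not help when two boxes fit equally well.

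**Conclusion.** The overlap is a fact of the printed form, at 6 months only. It gives an arbitrary value on a predictor the plan names, it falls short of the plan's own statement that time intervals were properly framed, and it cannot be undone from the data to be collected.

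Its statistical effect is probably negligible. With 5–10% of 300 children at 6 months and midway risk, making the boxes exclusive changes the odds ratio between them by 0.02 or less when the boxes' risks are 40% v 50%, and by 0.055 or less when they are 40% v 60%. The item's AUC changes by 0.002 or less even if the 6-month children carry the full 6–12 risk and split evenly. These results rest on assumed shares and risks.

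The effect on risk groups cannot be computed, because no scoring rule is given. It would be confined to 6-month children whose total lies close enough to a cut-off for one step on item 4 to matter. The documents do not support a claim that the tool's predictive ability or the primary analysis is threatened. This is a minor error in the data-collection form.

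**What to change.** Before data collection, relabel the boxes so that each duration fits one box, for example *under 3 måneder*, *3 til under 6 måneder*, *6 til 12 måneder*, *mere end 12 måneder*. Use identical labels on the paper, tablet and internet versions described in section 2.8.1. If any child has already completed the old wording, record the form version with the response.

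The cost is a label change: no new item, no extra completion time and no change to the analysis. The wording will differ slightly from the piloted form. The change makes answers of exactly 6 months consistent but does not remove rounding of recalled durations close to 6 months.
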